##### 9.7.1.6.3 EXPLORATORY EFFICACY ANALYSES

The number (percentage) of subjects with POS who achieved seizure-free during the 26-week Maintenance Period and the corresponding 95% confidence interval (CI) will be calculated by types of partial seizure.

The percent change in seizure frequency of POS per 28 days in the Maintenance Period and Extension Phase relative to the Pretreatment Phase will be summarized.

The change in EQ-5D-5L measurements from baseline to each postbaseline visit will be summarized.

#### 9.7.1.6.4 ANALYSIS AT PRIMARY ENDPOINT ACHIEVEMENT

If the primary endpoint is successfully achieved, statistical analysis of the Treatment Phase will be performed when all subjects end the 4 mg Maintenance Period.

At that time, the subjects who are continuing the 8 mg Treatment Phase will be regarded as non-seizure free, and their data until the latest visit will be analyzed. In addition, subsequent data after that will be regarded as data of the Extension Phase.

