### 9.7.1.1 Study Endpoints

#### 9.7.1.1.1 PRIMARY ENDPOINT

The primary endpoint is defined as follows.

- The seizure free rate in the 26-week Maintenance Period for subjects with POS

The number (percentage) of subjects with POS who achieved seizure-free during the 26-week Maintenance Period of 4 mg and regardless of perampanel dose will be calculated. For subjects who increase the perampanel dose from 4 mg to 8 mg, the seizure-free rate of the 26-week Maintenance Period of 8 mg will be evaluated to calculate the number (percentage) of subjects who achieved seizure-free regardless of perampanel dose.

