5.1 Study Endpoints

5.1.1 Primary Endpoint

The primary endpoint is defined as follows.

The seizure free rate in the 26-week Maintenance Period for subjects with POS

The number (percentage) of subjects with POS who achieved seizure-free during the 26-week Maintenance Period of 4 mg and regardless of perampanel dose will be calculated. For subjects who increase the perampanel dose from 4 mg to 8 mg, the seizure-free rate of

the 26-week Maintenance Period of 8 mg will be evaluated to calculate the number (percentage) of subjects who achieved seizure-free regardless of perampanel dose.

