5.4.2 Secondary Efficacy Analyses

The number (percentage) of subjects with POS who achieved seizure-free during the 26-week Maintenance Period regardless of perampanel dose and the exact corresponding 95% CI will be calculated. To examine if the 95% lower CI exceeds the threshold (ie, 40%) is the key secondary efficacy analysis. The 26-week Maintenance Period mentioned here is the Maintenance Period of the last evaluated dose (ie, 4 or 8mg).

The number (percentage) of subjects with POS who achieved seizure-free during the 52-week treatment of 4 mg (ie, 26-week Maintenance Period of 4 mg and 26-week Extension Phase) and the corresponding 95% CI will be calculated.

The number (percentage) of subjects with POS who achieved seizure-free during the 52-week treatment (ie, 26-week Maintenance Period and 26-week Extension Phase) and the corresponding 95% CI will be calculated. The 26-week Maintenance Period mentioned here is the Maintenance Period of the last evaluated dose.

Median, Q1 and Q3 time to first seizure onset will be estimated by Kaplan-Meier method. The cumulative probability of the event (ie, seizure occurrence) at every 26 weeks will also be calculated. Corresponding 2-sided 95% CIs will also be presented. Kaplan-Meier estimates of the time to event will be plotted over time. The Follow-up Phase will not be included in this analysis. The above analysis will be summarized for the entire study period of 4 mg and the entire study period of the last evaluated dose, respectively.

Time to first seizure onset will be defined as the period from the first dose of study drug in the Maintenance Period of the last evaluated dose to the first seizure onset. The censoring rule for the analysis of time to first seizure onset will be provide in the [section 8](#).

Median, Q1 and Q3 time to withdraw from the study will be estimated by Kaplan-Meier method. The cumulative probability of the event (ie, withdraw from the study) at every 26 weeks will also be calculated. Corresponding 2-sided 95% CIs will also be presented. Kaplan-Meier estimates of the time to event will be plotted over time. The Follow-up Phase will not be the period to be analyzed. The above analysis will be summarized for the entire study period of 4 mg and the entire study period of the last evaluated dose, respectively.

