5.4.3 Exploratory Efficacy Analyses

The number (percentage) of subjects with POS who achieved seizure-free during the entire study period and the corresponding 95% confidence interval (CI) will be calculated. The above analysis will also be summarized for the period between the Maintenance Period of the last evaluated dose and the date of data cutoff or the date of study discontinuation, whichever comes first.

The number (percentage) of subjects with POS who achieved seizure-free during the 26-week Maintenance Period of 4 mg and the 26-week Maintenance Period of the last

evaluated dose, and each corresponding 95% confidence interval (CI) will be calculated by types of partial seizure (ie, complex partial seizures, complex partial with secondarily generalized seizure, total of the 2 type).

The number (percentage) of subjects with POS who achieved seizure-free during the 52-week treatment of 4 mg (ie, 26-week Maintenance Period of 4 mg and 26-week Extension Phase) and the corresponding 95% CI will be calculated in subjects who had been scheduled to complete 52-week treatment and mITT analysis set. The above analysis will be performed by country, and will also be performed for subjects who completed 26-week maintenance period of 4 mg and did not enter extension phase excluded.

The number (percentage) of subjects with POS who achieved seizure-free during the 52-week treatment (ie, 26-week Maintenance Period and 26-week Extension Phase) and the corresponding 95% CI will be calculated in subjects who had been scheduled to complete 52-Week treatment and mITT analysis set. The 26-week Maintenance Period mentioned here is the Maintenance Period of the last evaluated dose. The above analysis will be performed by country, and will also be performed for subjects who completed 26-week maintenance period of 4 mg and did not enter extension phase excluded.

Median, Q1 and Q3 time to first seizure onset will be estimated by Kaplan-Meier method by country. The cumulative probability of the event (ie, seizure occurrence) at every 26 weeks will be calculated by country. Corresponding 2-sided 95% CIs will also be presented by country. The Follow-up Phase will not be included in this analysis. The above analysis will be summarized for the entire study period of 4 mg and the entire study period of the last evaluated dose, respectively.

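### Once the primary is met, subjects still in the 8 mg phase are scored as failures and no rule rescores them, so the key secondary any-dose rate is biased low for every eventual 8 mg success still ongoing at the cut.

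*Protocol*

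**What the plan says.** Protocol 9.7.1.6.4, repeated in SAP 3, applies only if the primary endpoint is achieved. The Treatment Phase is then analysed once every subject has ended 4 mg Maintenance. At that time "the subjects who are continuing the 8 mg Treatment Phase will be regarded as non-seizure free", and "subsequent data after that will be regarded as data of the Extension Phase".

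The any-dose endpoint is defined elsewhere by the full 8 mg period. For subjects who move from 4 mg to 8 mg, Protocol 9.7.1.1.1 says that "the seizure-free rate of the 26-week Maintenance Period of 8 mg will be evaluated", and SAP 5.1.1 agrees: "the 26-week Maintenance Period of 8 mg will be evaluated to calculate the number". For the key secondary rate and the overall 52-week rate, SAP 5.4.2 adds: "The 26-week Maintenance Period mentioned here is the Maintenance Period of the last evaluated dose". SAP 8.2 requires completion of the Treatment Phase at the last evaluated dose (seizures after Day 183 do not count) and scores everyone else non-seizure-free.

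The key secondary (Protocol 9.7.1.6.2) compares the lower 95% limit of the any-dose rate with 40% in the mITT set.

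**The concern.** A subject who is seizure-free at week 20 of 8 mg Maintenance at the cut is scored a failure only because the 26 weeks are not over. Neither document says that the score is revisited when they are, and moving the later data to the Extension Phase points against it. Whether an eventual 8 mg success counts then depends partly on enrolment date.

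At stake are the estimate and confidence interval of the key secondary, the binary rate that carries the 8 mg step of the design. By inference only, the 52-week rate at the last evaluated dose is affected in the same way: if the 26-week 8 mg status stays a failure, the 52-week definition cannot be met.

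**Working it through.** **The plan's own figures.** With N = 72 and success at 38 or more, the exact power at a true rate of 60% is 91.4%, which agrees with the stated figure of over 90%. The Clopper-Pearson lower limit is 40.65% for 38/72 and 39.31% for 37/72, so 38 is the minimum, as in Protocol Table 6.

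**Loss per subject.** 1/72 = 1.39 points.

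**Who is caught.** The 4 mg phase lasts 6 + 26 = 32 weeks and the 8 mg phase 4 + 26 = 30 weeks (Synopsis, Duration of Treatment). Assume that the cut falls when the last-enrolled subject reaches week 32 and that movers start 8 mg at once.
- A subject enrolled t weeks before the last one, with a seizure s weeks into 4 mg Maintenance, would complete 8 mg at week 6 + s + 30 of their own time. The cut comes at week 32 + t of that time.
- An eventual success is ongoing if 32 + t < 36 + s, that is, t < s + 4.
- Those enrolled in the last 4 weeks are always caught. Those enrolled more than 30 weeks before the last subject never are.

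**Fraction ongoing.** With uniform enrolment over E weeks (E at least 30), the fraction is p = (mean of s + 4)/E.

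| Timing of seizures on 4 mg (assumed) | mean s (weeks) | p, E = 52 | p, E = 104 |
|---|---|---|---|
| Even over 26 weeks | 13 | 17/52 = 0.327 | 17/104 = 0.163 |
| Early (exponential, mean 6, cut off at 26) | 5.65 | 9.65/52 = 0.186 | 9.65/104 = 0.093 |

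**Expected loss.** M movers × 8 mg success rate q × p / 72. Assume 43/72 seizure-free on 4 mg (about the planned 60%), so M is at most 72 − 43 = 29. I take M = 20 to 29 and q = 0.30.
- Even timing: lowest 20 × 0.30 × 0.163 = 0.98 subjects, 1.4 points; highest 29 × 0.30 × 0.327 = 2.84 subjects, 3.9 points.
- Early timing: lowest 20 × 0.30 × 0.093 = 0.56 subjects, 0.8 points; highest 29 × 0.30 × 0.186 = 1.62 subjects, 2.2 points.
- Even timing with q from 0.15 to 0.45: 0.7 to 5.9 points.

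**Effect on the 40% test.** The rule operates only if the primary is met, and both rates use the mITT denominator. The any-dose count is therefore at least the 4 mg count, with one exception: a subject who counts as a 4 mg success because the seizure came after Day 183, but who then moves to 8 mg and is ongoing. That changes the conclusion only at the margin (38 falls to 37 of 72). At a true rate of 60%, exactly 38 successes has probability 4.8% given that the primary is met, before the second condition is applied.

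**Do other planned analyses supply the corrected rate?**
- SAP 5.4.2: "The cumulative probability of the event (ie, seizure occurrence) at every 26 weeks will also be calculated". SAP 8.2 censors ongoing subjects there, but it also censors withdrawals, which the binary definition counts as failures. In a simulation of 3,000 trials with 24 movers, q = 0.30, even timing and 5 seizure-free withdrawals (all assumed), the rescored any-dose rate averaged 69.7%. The rate at the cut averaged 66.5% (E = 52) or 68.0% (E = 104), and the Kaplan-Meier 26-week seizure-free estimate about 78% or 77%.
- SAP 5.4.3 gives a rate over "the period between the Maintenance Period of the last evaluated dose and the date of data cutoff or the date of study discontinuation", a window with no fixed length.
- SAP 5.4.3 also gives 52-week rates "in subjects who had been scheduled to complete 52-week treatment and mITT analysis set". These are exploratory and leave the 26-week any-dose rate as it is.
- SAP 5.2.2 tabulates subjects ongoing in the 8 mg phase. That bounds the loss at (number ongoing)/N but does not give the corrected rate.

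**The case against.** The rule is pre-specified, was added by amendment, reads the same in both documents and is listed as the major addition in SAP 7. It errs against the drug, and counting incomplete follow-up as failure matches the default in SAP 8.2. The disposition table lets any reader bound the effect. In the simulation the rate at the cut lies below the rescored rate and the Kaplan-Meier estimate above it, so planned outputs bracket it; most of the Kaplan-Meier excess comes from the 5 assumed withdrawals (5/72 = 6.9 points), not from the cut. The loss is also small beside an interval about 24 points wide (43/72: 47.5% to 71.1%). All of this stands, and it is why the point is minor. It does not supply the missing statement of whether the score is final.

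A reader might infer more than the documents support:
- That the key secondary could fail because of the rule. Outside the boundary case above it cannot.
- That the primary or the 4 mg 52-week rate is affected. Neither uses 8 mg data.
- That the plan itself fixes the 52-week rate at the last evaluated dose too low. Protocol 9.7.1.6.4 concerns analysis of the Treatment Phase only. The 52-week effect follows from reading it with SAP 5.4.2 and 8.2, and no text says so outright.

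**Conclusion.** The point holds as a bias in an estimate. Followed as written, the plan understates the any-dose 26-week rate by 1/N (1.4 points at N = 72) for each eventual 8 mg success ongoing at the cut, and by nothing if there is none. The direction is certain, because the rule can only turn an eventual success into a failure. The size is not: enrolment time, number of movers, 8 mg success and seizure timing are all assumed. Under the ranges above the expected loss is about 1.4 to 3.9 points with evenly spread seizures and about 0.8 to 2.2 with early ones; enrolment faster than 52 weeks would raise it. The same effect on the 52-week rate at the last evaluated dose is an inference. Priority is minor, because an estimate and its interval are affected and pass/fail is not.

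**What to change.** Keep the early cut and its scoring rule for that analysis, and keep the phase labels for all other tables. Add to Protocol 9.7.1.6.4 and SAP 3:

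> The any-dose 26-week rate at this cut is preliminary. The number of subjects scored as failures only because they are ongoing on 8 mg will be shown beside it. At the final analysis this rate, and the last-evaluated-dose 52-week rate where it depends on it, will be re-derived under SAP 8.2 from diary data through 26 weeks of 8 mg Maintenance, whichever phase label the data carry. Subjects who change, before those 26 weeks are complete, to a dose outside the SAP 8.2 definition remain failures in this re-derivation, and their number will be reported. The rate at the cut and the re-derived rate will both be reported.

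The sentence on dose changes is needed because Protocol 9.1.3 allows dose adjustment in the Extension Phase. Diaries are returned and reviewed in both phases (Protocol Tables 4 and 5), so no new data are collected. Re-derivation can only add successes, so a 40% conclusion reached at the cut cannot be lost.

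The cost is this wording, one later table run, and two reported values for the key secondary, up to about 30 weeks apart (4 + 26).

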#### 9.7.1.7 Pharmacokinetic, Pharmacodynamic, Pharmacogenomic, and Other Biomarker Analyses

##### 9.7.1.7.1 PHARMACOKINETIC ANALYSES

The Safety Analysis Set will be used for pharmacokinetic analysis. Summary statistics of plasma perampanel concentrations will be obtained by visit.

##### 9.7.1.7.2 PHARMACODYNAMIC, PHARMACOGENOMIC, AND OTHER BIOMARKER ANALYSES

Not applicable.

#### 9.7.1.8 Safety Analyses

All safety analyses will be performed based on the Safety Analysis Set. Safety data will be summarized using descriptive statistics (eg, n, mean, standard deviation, median, minimum, maximum for continuous variables; n [%] for categorical variables). Safety variables include treatment-emergent adverse events (TEAEs), clinical laboratory parameters, vital signs, weight, and 12-lead ECG results. Study Day 1 for all safety analyses will be defined as the date of the first dose of study drug.

##### 9.7.1.8.1 EXTENT OF EXPOSURE

Extent of exposure to the study drug (eg, mean daily dose, maximum dose, last dose, duration of exposure) will be summarized using descriptive statistics. The exposure to the study drug will be classified by an appropriate category, and the number (percentage) of subjects will be summarized for the category, if necessary.

##### 9.7.1.8.2 ADVERSE EVENTS

The AE verbatim descriptions (investigator terms from the CRF) will be classified into standardized medical terminology using the Medical Dictionary for Regulatory Activities (MedDRA). Adverse events will be coded to the MedDRA (Version 19.1 or higher) lower level term (LLT) closest to the verbatim term. The linked MedDRA preferred term (PT) and primary system organ class (SOC) are also captured in the database.

A treatment-emergent adverse event (TEAE) is defined as an AE that emerges during time from the first dose of study drug to the last visit or 28 days after the subject's last dose, whichever comes later, having been absent at pretreatment (Baseline) or

- Reemerges during treatment, having been present at pretreatment (Baseline) but stopped before treatment, or
- Worsens in severity during treatment relative to the pretreatment state, when the AE is continuous.

Only those AEs that are treatment-emergent will be included in summary tables. All AEs, treatment-emergent or otherwise, will be presented in subject data listings.

The TEAEs will be summarized. The incidence of TEAEs will be reported as the number (percentage) of subjects with TEAEs by SOC and PT. A subject will be counted only once within an SOC and PT, even if the subject experienced more than 1 TEAE within a specific SOC and PT. The number (percentage) of subjects with TEAEs will also be summarized by maximum severity (mild, moderate, or severe).

The number (percentage) of subjects with treatment-related TEAEs will be summarized by SOC and PT. Treatment-related TEAEs include those events considered by the investigator to be related to study treatment. The number (percentage) of subjects with treatment-related TEAEs will also be summarized by maximum severity (mild, moderate, or severe).

A subject data listing of all AEs leading to death will be provided.

The number (percentage) of subjects with treatment-emergent serious adverse events (SAEs) will be summarized by MedDRA SOC and PT. A subject data listing of all SAEs will be provided.

The number (percentage) of subjects with TEAEs leading to discontinuation from study drug will be summarized by MedDRA SOC and PT. A subject data listing of all AEs leading to discontinuation from study drug will be provided.

The TEAEs will be summarized for the Treatment Phase and the entire study period (ie, the Treatment Phase or the Extension Phase).

#### 9.7.1.8.3 LABORATORY VALUES

Laboratory results will be summarized using Système International (SI) units, as appropriate. For all quantitative parameters, the actual value and the change from baseline to each postbaseline visit will be summarized by visit using descriptive statistics. Qualitative parameters will be summarized using frequencies (number and percentage of subjects), and changes from baseline to each postbaseline visit will be reported using shift tables. Percentages will be based on the number of subjects with both nonmissing baseline and relevant postbaseline results.

Laboratory test results will be assigned a low/normal/high (LNH) classification according to whether the value was below (L), within (N), or above (H) the laboratory parameter's reference range. Within-treatment comparisons for each laboratory parameter will be based on shift tables that compare the baseline LNH classification to the LNH classification at each postbaseline visit.

Appendix 1 (Sponsor's Grading for Laboratory Values) presents the criteria that will be used to identify subjects with treatment-emergent markedly abnormal laboratory values (TEMAVs). Except for phosphate, a TEMAV is defined as a postbaseline value with an increase from baseline to a grade of 2 or higher. For phosphate, a TEMAV was defined as a postbaseline value with an increase from baseline to a grade of 3 or higher. The definition of TEMAV will be detailed in the SAP. When displaying the incidence of TEMAVs, each subject may be counted once in the laboratory parameter high and in the laboratory parameter low categories, as applicable.

#### 9.7.1.8.4 VITAL SIGNS

Descriptive statistics for vital signs parameters (ie, systolic and diastolic blood pressure, pulse, respiratory rate, temperature) and weight; and changes from baseline will be presented by visit and treatment group.

#### 9.7.1.8.5 ELECTROCARDIOGRAMS

Shift tables will present changes from baseline in ECG interpretation (categorized as normal; abnormal, not clinically significant; and abnormal, clinically significant) by visit.

#### 9.7.1.8.6 OTHER SAFETY ANALYSES

Not applicable.

#### 9.7.1.9 Other Analyses

Not applicable.

### 9.7.2 Determination of Sample Size

In this study, perampanel will be determined to be efficacious if, in untreated subjects with POS (including secondary generalized seizures), the lower limit of the 95% confidence interval for the seizure-free rate in the 26-week Maintenance Period is above the pre-specified threshold (40%).

Based on the results from research papers of AEDs for mono-therapy ([Chadwick, et al., 1999](#), [Arroyo, et al., 2005](#), [Mikkelsen, et al., 1981](#), [Heller, et al., 1995](#), and [Kaneko, et al., 2015](#)), the expected seizure free rate for other AEDs would be assumed 50.0%. According to [Glauser, et al. \(2013\)](#), the relative difference >20% versus the adequate comparator's efficacy point estimate could be considered non-inferior margin if its 95% lower confidence limit was above this lower acceptable cutoff ([Glauser, et. al., 2013](#)).

Under the assumption that the expected seizure free rate of perampanel in the 26-week Maintenance Period would be 60%, sample size of 72 will provide greater than 90% power that the lower limit of the 95% confidence interval for the seizure free rate in the 26-week Maintenance Period is above 40%. Taking into consideration the drop-out rate in the Titration Period (approximately 10%), 80 subjects need to be as the ITT Analysis Set.

If the number of subjects who achieve seizure-free is above the following criteria, this study can declare to confirm the efficacy of perampanel.

**Table 6 Seizure free rate and 95% Confidence Interval**

| Target Number of mITT | Minimum Number of Subjects Who Achieve 26-week Seizure-free to Exceed the Pre-specified Threshold | Seizure-free Rate (95% CI) (%) a |
|-----------------------|---|---|
| 71                    | 38  | 53.5 (41.3, 65.5)                           |
| 72                    | 38  | 52.8 (40.7, 64.7)                           |
| 73                    | 38  | 52.1 (40.0, 63.9)                           |
| 74                    | 39  | 52.7 (40.7, 64.4)                           |
| 75                    | 39  | 52.0 (40.2, 63.7)                           |
| 76                    | 40  | 52.6 (40.8, 64.2)                           |
| 77                    | 40  | 51.9 (40.3, 63.5)                           |
| 78                    | 41  | 52.6 (40.9, 64.0)                           |
| 79                    | 41  | 51.9 (40.4, 63.3)                           |
| 80                    | 42  | 52.5 (41.0, 63.8)                           |
| 81                    | 42  | 51.9 (40.5, 63.1)                           |

CI = confidence interval, mITT = modified intent-to-treat.

a: 95%CI is based on Clopper-Pearson method.

